4.1.3. Exploratory effectiveness endpoints

The following exploratory endpoints will be evaluated:

- The difference in the proportions of subjects with TBUT > 10 sec at the follow-up, between eyes in the study arm and eyes in the control arm
- The difference in the proportions of subjects with OSDI < 23 at the follow-up, between subjects in the study arm and subjects in the control arm
- The difference in eyelids appearance at the follow-up, as qualitatively evaluated by the study investigator, between eyes in the study arm and eyes in the control arm
- The difference in the percentage of area loss of meibomian glands, as evaluated using meibography, between eyes in the study arm and eyes in the control arm
- The difference in the change of MGS from BL to FU, between eyes in the study arm and eyes in the control arm

where the *change* of a variable is defined as the value of this variable at the follow-up minus its value at the baseline.

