5.1.10. Meibography

Meibography of the upper and lower eyelids in both eyes will be performed using an ophthalmic imaging device with a built-in infra-red camera, such as Lipiscan/Lipiview (TearScience/Johnson & Johnson), Keratograph 5M (Oculus), Antares (CSO/Lumenis) or equivalent system. While the patient rests his/her head on the chin rest, the eyelid will be gently everted (turned over) using a cotton tip applicator, and an image of the eyelid will be captured.

The percentage of area loss of the meibomian glands will be evaluated using a 5-point scale, as illustrated in Figure 8: 0: no loss; 1: < 25 % loss; 2: 26%-50\% loss; 3: 51%-75\% loss; 4: > 75% loss.

Area of Loss

Meiboscale

Figure 8. Five-grade Meiboscale

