Safety Endpoints	At the treatment sessions-				
	 the difference in the change of bio-microscopy examinations pre- and post- treatment, between subjects in the study arm and subjects in the control arm 				
	• the difference in the self-assessment of pain/discomfort during IPL administration, between subjects in the study arm and subjects in the control arm				
	• the difference in the self-assessment of pain/discomfort during MGX, between subjects in the study arm and subjects in the control arm				
	Subjects will sign the IC form within one week of passing an informed consent process and having been provided the informed consent form (ICF). After signing the ICF, subjects will undergo the following baseline (BL) assessments, in the specified order:				
	1. Three consecutive measurements of tear break-up time (TBUT) in both eyes				
Corrections and	2. Routine ophthalmology tests in both eyes, including: biomicroscopy, best-corrected visual acuity (BCVA) and intra-ocular pressure (IOP)				
baseline (BL) visit	3. Ocular Surface Disease Index (OSDI), self-assessed using an OSDI questionnaire				
	4. Eye dryness score (EDS), self-assessed using a visual analog scale (VAS)				
	High resolution close-up photos of both eyes, including: the iris, lid margins and eyelashes				
	6. Meibography of the upper and lower eyelids in both eyes				
	7. Meibomian gland secretion (MGS) score in 15 glands of the lower eyelid in both eyes				
	Eligible subjects will be randomized 1:1 to a study arm or to a control arm				
Randomization	• The randomization process will adopt a blocked randomization strategy, using random block sizes of 2 and 4				
Treatment	Four (4) treatment sessions, 2 weeks (-3 days, + 7 days) apart.				
schedule	Each treatment session will consist of the following procedures, in the specified order:				

	 Subject's report of the daily usage (frequency and dose) of eye drops, warm compresses and lid hygiene since the previous visit 			
	Pre-treatment biomicroscopy with the slit lamp (observation of lid margins, eyelashes, conjunctiva)			
	3. In the study arm:			
	Active IPL administered on the malar region (from tragus to tragus, below the lower eyelids, including the nose)	-		
	In the control arm:			
	Sham IPL administered on the same facial areas			
	4. Meibomian gland expression (MGX) of the upper and lower eyelids in both eyes			
	5. Post-treatment biomicroscopy with the slit lamp			

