	6. Self-assessment of pain/discomfort during IPL administration, using a VAS			
	7. Self-assessment of pain/discomfort during MGX, using a VAS			
	There will be a single follow-up (FU) visit, which will occur 4 weeks (-3 days, + 7 days) after the final treatment session. Subjects will undergo the following assessments, in the specified order:			
	 Subject's report of the daily usage (frequency and dose) of eye drop, warm compresses and lid hygiene since the previous visit 			
	2. Three consecutive measurements of TBUT in both eyes			
Follow-up (FU)	3. Routine ophthalmology tests in both eyes, including: biomicroscopy, BCVA and IOP			
visit	4. OSDI, self-assessed using an OSDI questionnaire			
	5. EDS, self-assessed using a VAS			
	6. High resolution close-up photos of both eyes, including: iris, lid margins and eyelashes			
	7. Meibography of the upper and lower eyelids in both eyes			
	8. Meibomian gland secretion (MGS) score in 15 glands of the lower eyelid in both eyes			
Safety outcome measures	 incidence of non-ocular adverse events throughout the study incidence of ocular adverse events throughout the study incidence of unanticipated serious adverse events throughout the study self-assessment of pain/discomfort of IPL in treatment sessions (using a VAS) self-assessment of pain/discomfort of MGX in treatment sessions (using a VAS) 			
Covariates	Baseline TBUT (continuous)Baseline skin rosacea (4-point scale)			
	The following assumptions were used to calculate the original sample size:			
Sample Size	(1) In the study arm, the change of TBUT from BL to FU \approx 5 \pm 5 sec (2) In the control arm, the change of TBUT from BL to FU \approx 1 \pm 5 sec			

	(3) A type I error of 0.05 (two-tailed test)				
	(4) A type II error of 0.2 (power = 0.8)				
	(5) A 1:1 ratio of Treatment to Control				
	With these assumptions, the minimal sample size was calculated to be 50 evaluable subjects (100 evaluable eyes): 25 subjects (50 eyes) in the control arm and 25 subjects (50 eyes) in the study arm.				
	Assuming a dropout rate of 15%, the anticipated number of enrolled subjects was 59. Assuming a screening failure rate of 15%, the anticipated total number of screened subjects was 69.				

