2.4. Exploratory efficiency endpoints

- The difference in the proportions of eyes with TBUT > 10 sec (i.e., not consistent with DED) at the follow-up, between eyes in the study arm and eyes in the control arm
- The difference in the proportions of subjects with OSDI < 23 (i.e., not consistent with DED) at the follow-up, between subjects in the study arm and subjects in the control arm
- The difference in eyelids appearance, as qualitatively evaluated by the study investigator, between eyes in the study arm and eyes in the control arm
- The difference in the *change* of MGS, between eyes in the study arm and eyes in the control arm
- The difference in the *change* of Meiboscore (Meibography), between eyes in the study arm and eyes in the control arm

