5.7. Effectiveness analyses

The primary efficacy outcome measure (TBUT) consist of a pre-treatment measurement (the baseline), a treatment intervention, and a post-treatment measurement (the follow-up). Both eyes will be included in the analysis. Since the two eyes of a subject are not independent, to estimate whether TBUT has improved from the baseline to the follow-up, a linear mixed effects model with random intercept, using the subject identity as the random effect, is the appropriate test. Since there are two eyes per person then there is only one possible covariance structure (i.e. symmetric, with a single correlation between eyes).

The secondary efficacy outcome measures are OSDI and EDS which will be collected at the baseline, and at a follow-up visit. In the case of OSDI, the value is estimated per subject. Hence, a single value will be collected per subject at each of these two visits. In this case a paired t-test is the appropriate statistical test to estimate whether dry eye symptoms have improved, using the change of OSDI from baseline to the follow-up. In the case of EDS, the value is estimated per eye. Hence, two values will be collected per subject at each of these two visits. Since the two eyes of a subject are not independent, to estimate whether EDS has improved from the baseline to the follow-up, a linear mixed effects model with random intercept, using the subject identity as the random effect, is the appropriate test. The level of

statistical significance is $\alpha = 0.05$. Non-parametric tests will be performed if the underlying distributions are not normal.

For all other eye-level analyses, where appropriate, sample means of continuous variables will be analyzed with linear mixed effects model with random intercept (whenever both eyes of a subject are included in the analysis), or two-sample t-tests. Proportions will be analyzed with χ^2 tests.

All statistical tests will be two-sided because potentially the treatment procedure may worsen the outcome. The level of statistical significance (type I error) is $\alpha = 0.05$. Non-parametric tests will be performed if the underlying distribution is not normal.

For descriptive statistics, the N, Mean, Median, Standard deviation, Standard error of the mean, 95% confidence interval, Minimum, and Maximum will be reported for continuous variables; the frequency and proportion for each category will be reported for nominal and categorical variables.

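### The exploratory meibography endpoint is defined in two ways, and one definition names neither a change nor a time point, so it can be read as ignoring the baseline already collected

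*SAP*

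**What the plan says.** **Definition by change.** SAP 2.4 lists the between-arm difference in the change "of Meiboscore (Meibography), between eyes in the study arm and eyes in the control arm". Protocol 3.5.4 has the same item.

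**Definition by area loss.** SAP 4.1.3 lists "The difference in the percentage of area loss of meibomian glands, as evaluated using meibography", compared between eyes of the two arms. Protocol 6.1.3 and the exploratory list of the Protocol synopsis use the same words.

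**Neighbouring items in SAP 4.1.3.** The normal-TBUT, normal-OSDI and eyelid items are each fixed at follow-up; the eyelid item, for example, reads "The difference in eyelids appearance at the follow-up, as qualitatively evaluated by the study investigator". The gland-secretion item is fixed as a change: "The difference in the change of MGS from BL to FU, between eyes in the study arm and eyes in the control arm". Only the meibography item carries neither marker.

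**Measurement.** Protocol 5.1.10 states: "The percentage of area loss of the meibomian glands will be evaluated using a 5-point scale". Protocol 5.3.8 repeats this for follow-up. The SAP synopsis schedules the imaging at the baseline visit ("6. Meibography of the upper and lower eyelids in both eyes") and at the follow-up visit ("7. Meibography of the upper and lower eyelids in both eyes").

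**Analysis.** No model is written for meibography. The general rule in SAP 5.7 for other eye-level endpoints is that "sample means of continuous variables will be analyzed with linear mixed effects model with random intercept", or two-sample t-tests. That rule names no baseline covariate.

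**The concern.** Two statisticians working from the same SAP could analyse this endpoint differently. From SAP 2.4 one would compute follow-up minus baseline for each eye. From SAP 4.1.3 another could compare grades at follow-up alone. The estimates differ by whatever chance imbalance exists between the arms at baseline. Their standard errors differ too.

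The closing sentence of SAP 4.1.3 defines change as follow-up minus baseline, but it does not settle the matter, because the meibography item does not use that word. SAP 5.5, which calls for baseline summaries of the endpoints, does not name meibography among them, so an imbalance might not be displayed either. What is at stake is a clear, reproducible exploratory result, and the closing of a choice that could otherwise be made after unmasking.

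**Working it through.** **1. The definitions side by side**

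| Place | Quantity | Baseline used? | Time point given? |
|---|---|---|---|
| SAP 2.4, Protocol 3.5.4 | Meiboscore | Yes, as change | Implied by change |
| SAP 4.1.3, Protocol 6.1.3, Protocol synopsis | Percentage area loss | Not stated | Not stated |

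Under Protocol 5.1.10 and 5.3.8 area loss is recorded as a 0-4 grade. The two names therefore appear to describe one measurement, and the substantive difference is the use of baseline.

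**2. Precision of the possible readings**

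The plan gives no SD, power or correlation for meibography, so there is no figure of its own to reproduce. Assume equal SDs at both visits, the grade treated as a numeric score, and baseline-to-follow-up correlation r. Relative to a follow-up-only comparison (variance 1):

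- unadjusted change: 2(1 - r)
- baseline-adjusted: 1 - r²

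To put standard errors on the planned scale, take 83 subjects as 42 and 41, and a between-eye correlation of 0.5. SAP 5.3.2 states that correlation for the TBUT sample size; here it is assumed to apply to each version of the meibography outcome. The mean of two eyes has variance factor (1 + 0.5)/2 = 0.75, so

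SE = sqrt(0.75 × ratio × (1/42 + 1/41)), in units of one eye's SD.

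For follow-up only this is sqrt(0.75 × 0.0482) = 0.190.

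| r (assumed) | Variance ratio, change | Variance ratio, adjusted | SE, follow-up only | SE, change | SE, adjusted |
|---|---|---|---|---|---|
| 0.3 | 1.40 | 0.91 | 0.190 | 0.225 | 0.181 |
| 0.5 | 1.00 | 0.75 | 0.190 | 0.190 | 0.165 |
| 0.7 | 0.60 | 0.51 | 0.190 | 0.147 | 0.136 |
| 0.9 | 0.20 | 0.19 | 0.190 | 0.085 | 0.083 |

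Change beats follow-up only when 2(1 - r) < 1, that is, when r > 0.5. Adjustment is never worse than follow-up only, since 1 - r² ≤ 1. It is never worse than change, since 2(1 - r) - (1 - r²) = (1 - r)² ≥ 0. These are large-sample ratios; the one extra parameter costs little at this size.

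With baseline grade in the linear model, taking the follow-up grade or the change as outcome gives the same treatment estimate, because only the baseline coefficient shifts, by 1. The covariate therefore removes most of the ambiguity by itself.

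**3. Grade boundaries**

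Protocol 5.1.10 and 5.3.8 set grade 1 below 25%, grade 2 at 26-50%, grade 3 at 51-75% and grade 4 above 75%. Values from 25% to just under 26% have no grade, nor do values strictly between 50% and 51%. Exactly 75% is the top of grade 3, so there is no gap there. In whole percentages only 25% is left out.

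**The case against.** A reader might infer that SAP 4.1.3 prescribes a follow-up-only analysis. It does not. The neighbouring items that are meant at follow-up say so, and the meibography item does not. The defect is an unspecified time point, for which SAP 2.4 offers a definition. This stands: follow-up-only is one possible reading, not a stated plan.

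A reader might also infer that precision is necessarily lost against the change score. That is conditional. At r = 0.3 the change score has 1.40 times the follow-up-only variance, so the SAP 2.4 definition would be the less precise of the two. A high r is plausible for gland structure over about ten weeks, but that is an assumption, and coarse five-grade scoring could lower it. Only the gain from baseline adjustment holds for any non-zero r, and neither definition specifies adjustment for this endpoint.

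Three further inferences lack support.

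- Percentage loss and Meiboscore are not shown to be separate measurements, since the loss is graded on the same scale.
- Nothing shows that gland loss varies widely at entry. The criterion of at least five non-atrophied lower-lid glands in the study eye (Protocol 4.2.1) gives no distribution.
- The area-loss item is readable in the Protocol synopsis. It is not visible in the SAP synopsis text available for review, where the table is broken, so nothing is claimed about that synopsis.

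Finally, the endpoint is exploratory. That stands, and it limits the importance of the point.

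**Conclusion.** The inconsistency is real, lies in current text of both documents, and needs no assumption to establish: one endpoint is defined as a change in one place and without change or time point in another. It is minor. The success criterion in SAP 2.2 concerns TBUT only and is untouched.

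The possible cost in precision depends on r, which is not given. Against baseline adjustment, a follow-up-only comparison would have 1/0.91 = 1.10, 1/0.75 = 1.33, 1/0.51 = 1.96 or 1/0.19 = 5.26 times the variance at r = 0.3, 0.5, 0.7 or 0.9. These figures assume equal SDs at the two visits and a grade treated as numeric. The documents support neither a claim that such a comparison is planned nor a claim that change alone is always better. They do support fixing one baseline-adjusted definition, which uses data already scheduled. The gaps in the grade boundaries are a separate, smaller defect in the same endpoint.

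**What to change.** 1. Use one definition in SAP 2.4 and 4.1.3, Protocol 3.5.4 and 6.1.3, and the Protocol synopsis: the between-arm difference in change of Meiboscale grade (0-4) from baseline to follow-up. Check the SAP synopsis for the same item.
2. State the analysis: the eye-level random-intercept mixed model of SAP 5.7, with treatment and that eye's baseline grade as fixed effects. This is the form SAP 5.7.2 already uses for TBUT.
3. State how upper- and lower-lid grades make one value per eye. Both lids are imaged, so without a rule the eye-level outcome is undefined. The mean of the two lids would keep the 0-4 range.
4. Make the grade boundaries in Protocol 5.1.10 and 5.3.8 contiguous and consistent with Figure 8.
5. Name meibography among the baseline summaries in SAP 5.5.

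No visit, image or subject is added. The SAP changes are wording and one model term. The Protocol changes are an amendment, which under Protocol 9.7 needs the sponsor's written agreement and IRB approval. The definition should be fixed before unmasking.

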4.2. Safety

Safety will be assessed by reporting:

- The difference in the incidence of related adverse events, between subjects in the treatment arm and subjects in the control arm
- The difference in the incidence of unrelated adverse events, between subjects in the treatment arm and subjects in the control arm
- The difference in the level of pain/discomfort during IPL treatment, between subjects in the treatment arm and subjects in the control arm
- The difference in the level of pain/discomfort during MGX, between subjects in the treatment arm and subjects in the control arm

5. Study Analysis Plan

5.1. Primary Study Hypothesis

The *change* of TBUT (Δ TBUT) in eyes of the study arm is *more positive* than Δ TBUT in eyes of the control arm, where Δ TBUT is defined as TBUT at the follow-up minus TBUT at the baseline, and subscripts S, C indicate the study (S) or control (C) arms:

H0: $\Delta TBUT_{s} \leq \Delta TBUT_{c}$

H1: $\Delta TBUT_{S} > \Delta TBUT_{C}$

5.2. Secondary Study Hypotheses

 The change of OSDI (△OSDI) in subjects of the study arm is *more negative* than △OSDI in subjects of the control arm, where △OSDI is defined as OSDI at the follow-up minus OSDI at the baseline:

H0: $\triangle OSDI_S \ge \triangle OSDI_C$

H1: $\triangle OSDI_S < \triangle OSDI_C$

 The change of EDS (△EDS) in subjects of the study arm is *more negative* than △EDS in subjects of the control arm, where △EDS is defined as EDS at the follow-up minus EDS at the baseline:

> H0: $\triangle EDS_{S} \ge \triangle EDS_{C}$ H1: $\triangle EDS_{S} < \triangle EDS_{C}$

5.3. Sample Size

Approximately 4 months after initiation of the study, a round of site monitoring visits revealed that one of the three sites in the study was not following the instructions above with respect to where the M22 IPL lightguide should be applied; for IPL and sham subjects the lightguide was being applied too far from the eyelid margin in contrast to what is described in Figure 5 above. As a result, it is possible that the IPL treatments among the initial cohort of subjects at that site was will prove to be ineffective, or of reduced effectiveness compared to the sham control. The lightguide was applied correctly at the other two sites.

Although no data were unmasked, soon after this issue was recognized by study monitors, Lumenis initiated a corrective action (retraining and greater emphasis in the protocol), to better assure the protocol instructions would be followed.

To restore the original statistical power, the sample size was increased. Below are the original and adjusted calculations of the sample size:

5.3.1. Original calculation of the sample size

Assuming a 1:1 randomization ratio, a mean of 5 ± 5 sec for \triangle TBUT of the study arm, a mean of 1 ± 5 sec for \triangle TBUT of the control arm, an alpha level of 0.05 and a power of 80%, the total sample size is 50 completed study eyes (25 for the study arm and 25 for the control arm). Assuming a dropout rate of 15%, the anticipated number of enrolled subjects is 58. Assuming a screening failure rate of 15%, the anticipated total number of screened subjects is 66.

In addition, MGD is less common without concomitant skin rosacea. Therefore, enrollment will continue until at least 10 subjects without skin rosacea are enrolled, even if 58 subjects were already enrolled.

5.3.2. Adjusted calculation of the sample size.

After the corrective action to remedy the treatment errors, the sample size was recalculated using a simulation where we made the following conservative assumptions:

- The initial 8 IPL subjects at the affected site had response equal to the control arm (1±5 seconds)
- Subsequent to the corrective action, IPL subjects at the affected site had a response equal to the IPL arm (5±5 seconds)
- The final analysis was ITT, which included the inappropriately treated patients in the IPL arm.
- The correlation between eyes within a subject is 0.5.

Under these assumptions the overall treatment effect is "diluted" by the initial set of patients who were treated inappropriately. Under these conservative assumptions, the sample size needed to restore the original power was calculated to be 136 evaluable eyes (68 subjects, i.e. 18 subjects more than the original 50 subjects).

In addition, in order to allow for full comparison of the effect of the corrective action, 15 patients were added to the enrollment at the affected site so there would be sufficient before/after patients to allow for clinical evaluation of the difference.

Adding these 33 (18+15) subjects to the original 50 completed subjects, the number of completed subjects is up to 83. Therefore, with a loss to follow-up rate of 7% the expected number of enrolled subjects is 89, and with a screening failure rate of 23% the expected number of screened subjects is 116.

All sample size re-calculations were done prior to any unmasking of any results from the study.

5.4. Subject Accountability

A complete accounting of subjects by Treatment Arm and visit will be provided, including reasons for dropout, if known.

5.5. Demographics and Baseline Characteristics

Demographic variables gender, race, ethnicity, and age will be summarized for all enrolled subjects, along with medical history, by Treatment Arm and combined. Descriptive statistical summaries of pre-treatment parameters (min, max, median, mean, standard deviation) will also be provided for each treatment arm. This includes baseline measurements for each of the study endpoints: TBUT, Total Meibomian Gland Secretion Score, OSDI Score, and Eye Dryness VAS Score, as well as Fitzpatrick skin type and skin rosacea.

All baseline measurements will be evaluated for adequate balance between the two treatment arms.

